3.0. STUDY DESIGN AND TREATMENT

3.1 STUDY OUTCOMES/ENDPOINTS

Key study outcomes/endpoints are listed below:

- Efficacy. Mucositis scores in 4 standard mucositis scales.
- PD: Evaluation potential relationships among TK-112690 dose, mucositis scores, and surrogate markers of mucositis, e.g., CD40/CD40Land TNF-α.

[figure not shown]
3.1.2. DOSE MODIFICATIONS

[figure not shown]
Treatment will be withheld following grade 3 or 4 adverse events. Treatment may be restarted when the adverse events have recovered to \leq grade 2. Subjects in whom treatment is withheld for > 2 weeks will have treatment discontinued permanently.

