- Study follow-up will occur on Week 6, two weeks after the last dosing of MTX.
- Blinding: The study will be partially blinded. The patient and investigator will be blinded as to whether TK-112690 or placebo is administered. The CRO,sponsor, and site pharmacist will know whether the patient was administered active drug or placebo.

Main Study Endpoints/Outcomes

• Mucositis Outcomes

Mucositis status in the patients will be evaluated using 4 different published and validated mucosit scales: OMAS/Sonis, PROMS, WHO, and CTCAE/mucositis.

• Surrogate Marker Outcomes

Plasma samples will be obtained to determine surrogate markers of mucositis, eg, CD40/CD40. TNF- α , etc.

• Safety Outcomes

Adverse events will be assessed throughout the study. Incidents of toxicity will be determined to at least possibly related to the study drug and graded according to CTCAE Version 4.0.

Study Procedures and Study Assessments

- A review of a patient's medical history including a detailed history of the patient's cancer and concomitant medications will be performed at screening.
- Screening for drugs of abuse will be performed at the time of patient screening and Day 0 (the day before start of study).
- Vital sign measurements will be performed at patient screening, on Day 0, and at 24 and 48

hours post each initial infusion of TK-112690/placebo as well as on Day 1 of Week 6.

- Physical examinations will be performed at screening, on Day 0, and 24 and 48 hours post each initial infusion of TK-112690/ placebo as well as on Day 1 of Week 6.
- ECOG performance status will be determined at patient screening, on Day 0, and at Day 1 of Weeks 6.
- For pre-menopausal females, a urine pregnancy test will be performed at screening, on Day 0, and at Day 1 of Week 6.
- 12-Lead ECG at screening and 24 hours post each initial infusion of TK-112690/ Placebo.
- CBC, Liver function test, Kidney function test determination at the clinical site prior to methotrexate treatment to ensure patient fit to dose.
- Serum chemistry, hematology, coagulation and urinalysis at screening, Day 0, and at 24 and 48 hours post each initial infusion of TK-112690/ placebo as well as on Day 1 of Week 6.
- Adverse events will be evaluated 5, 24 and 48 hours post each initial infusion of TK-112690/ Placebo as well as on Day 1 of Week 6.

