- Blood samples will be obtained pre-initial infusion of TK-112690/ placebo and 5, 24 and 48 hours post each initial infusion as well as on Day 1 of Week 6. Plasma will be obtained from the blood samples in order to determine surrogate markers of mucositis, e.g., CD40/CD40L, TNF- α , etc.
- Patients will be evaluated for extent and severity of mucositis using established mucositis rating scales, e.g., OMAS/Sonis, PROMS, WHO, and CTCAE/mucositis on the day prior to study start (Day 0), and 24 and 48 hours post each initial infusion of TK-112690/ placebo as well as on Day 1 of Week 6. Examination will assess the lining of the mouth, throat, and other linings of the digestive tract. Incidence of oral mucositis, duration of severe oral mucositis, throat soreness, severity of pain and use of parenteral or transdermal opioid analgesics will be assessed.

Study Population

Patients at least 18 years old, diagnosed with locally advanced or residual or recurrent or metastatic SCCHN and scheduled to receive 45 mg/m² MTX to treat their cancer. The diagnosis must be confirmed by histopathology or cytology.

Inclusion Criteria

- Male and female subjects over 18 years old with a histologically or cytological confirmed diagnosis of locally residual, recurrent or metastatic SCCHN.
- Subject must have failed at least onecourses of non-MTX chemotherapy, orone course of non-MTX chemotherapyand chemo radiation for treating their SCCHN.
- No prior systemic treatments for cancer (chemotherapy and/or radiotherapy) 4 weeks prior to screening.
- No other concurrent, active, invasive malignancies.
- An Eastern Cooperative Oncology Group (ECOG) performance status of 0 to 2.
- Must have a life expectancy of at least 6 months.
- History of brain metastases allowed if disease has stabilized or improved after radiation and/or craniotomy.
- No active angina or uncontrolled arrhythmia.
- No detectable infection including hepatitis B/C and HIV.
- Not pregnant or nursing. Women of childbearing potential must have a negative urine pregnancy

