- Subjects that have participated in any other investigative clinical trial in the past 4 weeks.

Dose and Dosing Regimen

The dose of METREXASSISTTM (TK-112690) will be 45 mg/kg administered parenterally over one hour in a clear, neutral, aqueous formulation (no organic chemical excipients). METREXASSISTTM will be given one hour before and 5 hours after the MTX treatment. The nutrient drink will be given one hour before METREXASSISTTM infusion. The MTX formulation will that traditionally used as standard-of-

care at a study site.

Test Product, Dose and Mode of Administration

- METREXASSISTTM (TK-112690 for Infusion) is a clear, sterile, neutral (pH=7.4), aqueous solution containing 5 mL of 100 mg/mL TK-112690.
- METREXASSISTTM is packaged as a 5 mL solution in a 10 mL flint glass vial with an elastomeric stopper held in place by an aluminum seal and flip-off cap. The concentration of TK-112690 in the solution is 100 mg/mL
- METREXASSISTTM will be administered as a continuous iv infusion over a duration of one hour in a volume of 250 mL normal saline.
- The nutrient drink, Fortasyn Connect[™] / Souvenaid[™], is commercially available as a 125 mL, 125 kcal solution. The drink is administered orally.
- The placebo is isotonic saline.

Reference Therapy or Comparator

Placebo-Isotonic saline

Follow-up

[figure not shown]
Subjects need to return at Day 1 of Week 6, which is two weeks from the last dose of the study drug.

Statistical Methods

- Safety: AEs, vital signs, physical examination data and clinical laboratory data will be analyzed using descriptive statistics with safety outcomes for patients in a dose group pooled & compared with patients in other groups.
- Mucositis: Scale data from individual doses groups will be analyzed using descriptive statistics.
- Surrogate Markers: Plasma concentration data evaluated for individual doses groups using descriptive statistics as well as compared with Surrogate marker data from the completed Phase 1bstudy.

INTRODUCTION

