5.2. STUDY THERAPY ADMINISTRATION

The study therapy will be administered as an infusion via a peripheral vein in the forearm delivered using a catheter. This access vein for the infusion must not be used for blood sampling. Replacement of the intravenous catheter will be done according to local practice and the discretion of PI or designee, e.g., in the event of phlebitis. If a catheter is replaced, it should be flushed with saline prior to removal unless there are signs of phlebitis. TK-112690/placebo will initially be administered as a one-hour infusion. In case of immediate adverse reaction to the infusion, please follow management of reaction (Appendix 4: Infusion Reaction Criteria).

Epinephrine (1:1000) for subcutaneous injection, diphenhydramine (12.5 mg to 50 mg) for iv injection, and any other medications and resuscitation equipment for the emergency management of anaphylactic reactions must be available in the room where the infusions are being performed.

All patients will be evaluated at a follow-up visit on Day 1 of Week 6 post after initial drug treatments.

METREXASSISTTM (TK-112690 for Injection) should be prepared for infusion by a healthcare professional using aseptic technique. METREXASSISTTM will be diluted into 250 mL of 0.9% sodium chloride in a iv bag/bottle. Please refer to **Appendix 3** for the directions on how to calculate and dilute for the different doses to be administered to the subjects.

For the placebo will be prepared as described above for the TK-112690 except isotonic saline in 10 mL glass vials will be substituted for the 10 mL METREXASSISTTM vials.

Dosing will be calculated on a mg/kg basis and rounded to the closest 10 mg. The TK-112690/placebo dose will be 45 mg/kg.

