7.1.3. Days 1 and 2 (Weeks 1-4)

Patients will be hospitalized on Day 1 and observed until after the 25-hour evaluations and plasma sample collection are obtained. All subjects will undergo the following on Days 1 and 2 of Weeks 1-4:

- An in-house CBC, Kidney function test, Liver Function test to be performed within 24 hours of expected methotrexate dosing to verify patient Fit to receive methotrexate.
- The nutritional supplement is ingested 2 hours prior to initiation of the MTX treatment, one hour prior to the TK-112690/placebo infusion.
- TK-112690/placebo is administered as a one hour infusion pre-MTX and 5 hours post-MTX (±15mins window period).
- One hour after the initial infusion of TK-112690 or placebo, MTX will be administered by continuous infusion for one hour (±15mins window period).
- Physical examination, vital signs, weight, mucositis evaluation at 24 and 48 hours post the initialTK-112690/placebo infusion.
- 12-lead ECG at 24 hours post initial TK-112690/placebo infusion.
- Laboratory tests (hematology, chemistry, coagulation and urinalysis) 24 and 48 hours post initial TK-112690/placebo infusion.

- Plasma samples will be collected for surrogate marker measurements pre-dose of the nutraceutical and 5, 24 and 48 hours initial infusion of TK-112690 orplacebo.
- Mucositis assessments (Section 20.6, Appendix 6) at 24 and 48 hours post initial infusion TK-112690 or placebo.
- AEs to be recorded at 5, 24 and 48 hours post initial infusion of TK-112690 or placebo.
- ± 15 mins of window period is considered acceptable for schedule of events.

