7.1.4. Follow-Up Evaluations

All patients will undergo the following on Day 1 of Week 6:

- Perform a physical examination and determine vital signs, weight, and AE assessment.
- Determine ECOG performance status.
- For females of childbearing age, a pregnancy test will be performed.
- Perform laboratory tests (hematology, chemistry, coagulation and urinalysis).
- Obtain a blood sample for surrogate marker evaluation.
- Disease (tumor) assessment by CT scanning will be performed.
- Mucositis assessment (Section 20.6, Appendix 6).

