8.2. SUBJECT WITHDRAWAL CRITERIA

A subject may voluntarily discontinue study participation at any time. At any time, the PI may also at his/her discretion discontinue a subject's study participation. Subjects may be withdrawn from this study for the following reasons:

- At the PI's discretion in situations where the subject is unable to comply, or complies poorly with the protocol.
- Disease progression and/or experiences intolerable toxicity.
- Major protocol violation.
- Lost to follow-up.
- If TK-112690/placebo treatment is delayed due to toxicity for more than 2 weeks.
- Inter-current event preventing administration of study medication for more than 2 weeks.
- Subject withdraws consent.
- Subject becomes pregnant.
- Subject starts any other chemotherapy agent or anti-cancer treatment other than study therapy for refractory solid tumor, e.g., radiation therapy.

• Death.

If there is an ongoing toxicity due to the study agent, subjects must be followed with appropriate medical management until resolution or stabilization, regardless of evidence of progressive disease.

The subject will be advised in the Informed Consent Forms that he/she has the right to withdraw from the study at any time without prejudice and may be withdrawn at the discretion of the PI or Tosk at any time. In the event that the subject drops out of the study or is withdrawn from the study, the withdrawal CRF should be completed. On the withdrawal page the PI should record the date of the withdrawal, the person who initiated withdrawal and the reason for withdrawal.

Reasonable effort should be made to contact any subject lost to follow-up during the course of the study in order to complete assessments and retrieve any outstanding data.

At the time of study withdrawal, following will be recorded for these premature removals:

- Update medical history including any additional cancer therapies, including starting date (immunotherapy, targeted therapy, radiation and surgical interventions) if known.
- Physical examination and determination of vital signs, weight and AEs.
- Laboratory tests (hematology, chemistry, coagulation and urinalysis).
- Mucositis assessment (Section 20.6, Appendix 6).

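### No mucositis score is scheduled while a dose is held for toxicity, so OMAS and WHO, and PROMS in part, can miss some of a severe episode

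*Combined protocol and SAP*

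**What the plan says.** **Holds.** Section 3.1.2 (Dose Modifications) withholds treatment after any grade 3 or 4 adverse event, permits restart once the event is at grade 2 or lower, and caps the hold: "Subjects in whom treatment is withheld for > 2 weeks will have treatment discontinued permanently". Section 8.2 speaks of treatment being delayed by toxicity, which points to postponement. No section says whether a held dose is made up or skipped.

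**Scores.** The synopsis (Study Procedures and Study Assessments) places the four scales "on the day prior to study start (Day 0), and 24 and 48 hours post each initial infusion", and again on Day 1 of Week 6. Section 7.1.3 repeats the on-treatment times: "at 24 and 48 hours post initial infusion TK-112690 or placebo". Table 12 defines hour 0 as the start of the infusion. Section 8.2 adds a mucositis assessment for patients who leave: "At the time of study withdrawal, following will be recorded for these premature removals". Section 3.1 makes scores on the four scales the efficacy outcome, and the synopsis lists how long severe oral mucositis lasts among the things to be assessed.

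**Follow-up.** Section 5.2: "All patients will be evaluated at a follow-up visit on Day 1 of Week 6 post after initial drug treatments". Section 7.1.4: "All patients will undergo the following on Day 1 of Week 6". The synopsis ties the same visit to the last dose, under Study Design ("Study follow-up will occur on Week 6, two weeks after the last dosing of MTX") and under Follow-up ("Subjects need to return at Day 1 of Week 6, which is two weeks from the last dose of the study drug").

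**The concern.** A withheld infusion has no 24- or 48-hour time point, so the schedule creates no score in that week. When mucositis is the reason for the hold, the restart rule places the next on-treatment score after the event has fallen to grade 2 or less. OMAS and WHO describe the mouth on the day of examination, so nothing later recovers what they would have shown during the hold.

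The loss would probably not be equal between arms. Section 10.1.1 expects considerably more mucositis without TK-112690. Holds caused by mucositis would then fall mainly on placebo, and the missing scores would be the high ones, so the difference between arms would be understated. Section 10.1.1 also intends these data to power the next study, so an understated difference would carry forward. Holds for other causes have no expected direction.

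A smaller matter is that the follow-up visit has two anchors. They agree when dosing is on time and separate when it is not.

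**Working it through.** **Inputs.** Weekly dosing for four weeks (section 3.2) gives dose days 1, 8, 15 and 22. Day 1 of Week 6 is 1 + 5 × 7 = day 36. A single hold lasts h days, up to 14 (section 3.1.2). The ten PROMS items in Appendix 6 recall the past week, taken as 7 days. I assume postponed doses keep weekly spacing afterwards.

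**1. The plan's own figure.** 36 − 22 = 14 days. The two follow-up anchors agree when no dose moves.

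**2. Interval between scores.** After a dose on day d, the 48-hour score is on d + 2. The next dose is on d + 7 + h and its 24-hour score on d + 8 + h. The interval is (d + 8 + h) − (d + 2) = 6 + h.

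**3. PROMS cover within the hold.** Recall at the score on d + 8 + h reaches back to d + 1 + h. The hold began on d + 7. Hold days not covered: max(0, (d + 1 + h) − (d + 7)) = max(0, h − 6).

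**4. Follow-up anchors.** The last MTX is on day 22 + h, so two weeks later is day 36 + h. The anchors differ by h, and Day 1 of Week 6 falls 14 − h days after the last MTX.

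| Hold | Interval between scores | Hold days outside PROMS recall | Last MTX + 14 | Day 36 minus last MTX |
|---|---|---|---|---|
| none | 6 days | 0 | day 36 | 14 days |
| 7 days | 13 days | 1 | day 43 | 7 days |
| 14 days | 20 days | 8 | day 50 | 0 days |

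Restart depends on recovery, so h can be any value from 1 to 14, and repeated holds add up because no cumulative cap is given. If held doses are skipped instead, the anchors differ only when dose 4 is lost: by −7 days, or −14 if dose 3 is lost as well.

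**5. How many patients.** Section 1.5.2.3 reports 6 grade 3/4 events in 5 of 25 Phase 1b patients, and section 1.5.2.7 describes five as hematologic.
- Non-hematologic events: 6 − 5 = 1, so at most 1/25 = 4% (95% Clopper-Pearson 0.1% to 20.4%). For 11 TK-112690 patients: 0.04 × 11 = 0.44, upper limit 0.204 × 11 = 2.2.
- Placebo: no rate is given. Assumed rates of 10%, 20% or 30% for grade 3/4 mucositis give 1.1, 2.2 or 3.3 of 11.
- Holds for any cause: 5/25 = 20% (6.8% to 40.7%), × 22 = 4.4 patients (1.5 to 9.0), nearly all hematologic. Four Phase 1b patients stopped for anemia and two died, so fewer than this would restart.

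**The case against.** **The schedule may still require visits in a held week.** Section 7.1.3 opens by applying its list to all subjects in Weeks 1-4, section 7.0 wants visits on the indicated day, and section 3.1.2 withholds treatment, not visits. A site could read this as keeping the scores. But the mucositis items in that list are timed from the initial infusion, and Table 12 starts the clock there. The general opening does not supply a time when there is no infusion.

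**The severe phase is not always missed.** This stands. An event already present at a 24- or 48-hour visit is scored before the hold. Patients withdrawn are scored under section 8.2, and a late hold may run into the Week 6 score. A reader might infer that all scales lose every severe episode in a hold; the documents do not support that. The AE form keeps a dated CTCAE grade (sections 9.1.1, 9.1.4 and 9.3), so CTCAE incidence and duration survive.

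**PROMS recall covers much of the hold.** This also stands. Subtracting 7 from the whole interval gives 13 − 7 = 6 or 20 − 7 = 13 uncovered days, but 5 of those lie before the held dose was due. Only 1 or 8 fall within the hold.

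**Few patients, exploratory trial.** Correct as to numbers. Phase 1b gives no count of patients held and restarted, and the analysis is descriptive. That limits the size of the point but does not remove it, because one to three severe placebo episodes would matter with 11 per arm.

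**The follow-up anchors are the same visit.** The synopsis equates them, and Table 12's weekly-cycle heading lets week numbers move with dosing. A reader might infer a contradiction in the plan. It is rather an unstated rule that matters only after a dose moves.

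**Conclusion.** The scoring gap is in the text and is worth closing. With a 1- or 2-week hold the interval between scheduled scores rises from 6 days to 13 or 20. If mucositis is the cause, OMAS and WHO can miss part of the severe phase, and PROMS about 1 or 8 days of the hold.

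The number affected is probably small: at most about 0.4 of 11 on TK-112690, and an unknown number on placebo (1.1 to 3.3 of 11 under the assumed 10-30%). The direction, towards understating the difference, rests on the expectation in section 10.1.1. The size of any bias cannot be estimated from the documents. The 7- and 14-day follow-up shifts assume that doses are postponed and restarted on the weekly grid. The follow-up part is a clarification only.

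**What to change.** **Scores.** In section 7.1.3 and Table 12, state that when a dose is withheld all four scales are still scored at that week's nominal 24- and 48-hour times, or at least once per held week, until restart or withdrawal. Both arms then keep the same calendar frequency of assessment.

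**Analysis.** State that these scores enter the by-arm mucositis summaries for all randomized and dosed patients, shown beside the efficacy population of section 10.2.1. That population requires at least four doses. Dosing is twice per treatment day, so if each infusion counts as a dose, a patient stopped after Week 1 has had two and is left out whatever scores are added.

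**Follow-up.** Patients who complete postponed doses are seen 14 days (± 1) after the last MTX. Patients permanently discontinued have the section 8.2 withdrawal score and keep Day 1 of Week 6. One rule of 14 days after the last MTX for everyone would not work. With MTX on day 8 and the next dose due on day 15, restart is allowed until day 29, yet the visit would fall on day 22, while the hold is still open.

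**Cost.** Planned examinations number 22 × (1 + 8 + 1) = 220. At two per held week, one hold of one or two weeks adds 2 to 4 per held patient: 4.4 × 2 = 8.8 to 4.4 × 4 = 17.6, or 4% to 8%. One per held week halves this; repeated holds raise it. These are extra visits for patients who are unwell, which is the reason to allow the once-weekly minimum. Postponed patients have a later follow-up visit, and its CT scan, laboratory tests and marker sample move with it. At 14 days after the last dose it remains inside the 28 days of AE follow-up in section 9.1.4.

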3.2. OVERVIEW OF STUDY DESIGN AND DOSING REGIMEN

This is a multi-center, randomized, partially blinded, placebo controlled, Phase 2a, pilot efficacy/safety study of $METREXASSIST^{TM}$ (parenteral TK-112690) administered weekly for 4 weeks in combination with MTX in subjects with SCCHN.

Figure 20 below provide, respectively, an overview of the study design.

3.3 CONCOMITANT MEDICATION AND TREATMENT

Subjects should continue at study initiation with their concomitant medications, as directed by their physicians. Any medication or therapy received by the patient within 4 weeks of baseline, during the study, including: over-the-counter, herbal preparations, supplements, prescription and non-prescription drugs, vaccinations or discontinued medications must be reported on the appropriate concomitant

medication page(s) of the case report form (CRF). The information on the concomitant medication/therapy CRFs will include the name of the medication/therapy, dose, frequency, route of administration, dates of use (start and finish date), and indication for use. Subjects should be instructed not to take any medications including over-the-counter products, without first consulting with the PI. Any adverse event that results from taking a concomitant medication/therapy should be recorded on the CRF adverse event page. Additionally, any diagnostic, therapeutic or surgical procedure performed during the study period, should be recorded including date, indication, description of the procedure and any clinical findings.

